### 6.2.1. **Unscheduled Visits**

Unscheduled visits, if needed, may occur at any time, in particular for safety reasons (or efficacy reasons) as deemed necessary by the Investigator or site staff, or for any reason that the subject must return to study center as it pertains to the study (eg, to pick up additional or replacement IP). All assessments contained in [Table 3](#) will be made available to the site staff in the Unscheduled Visit eCRF, in order to perform the necessary unscheduled assessments and/or procedures.

### 6.3. **Early Termination**

An Early Termination (ET) evaluation will be performed for subjects who are withdrawn from study treatment for any reason at any time other than the Week 12 Visit, including subjects who early escape into the Long-term Active-treatment Study, as soon as possible after the decision to permanently discontinue study treatment has been made. (Subjects who discontinue from study treatment at Week 12 will complete the Week 12 Visit.)

The following evaluations will be performed as specified in [Table 3](#):

- Prior and concomitant procedures
- Prior and concomitant medications
- AE evaluation (continuously assessed)
- 12-lead ECG
- A urine pregnancy test will be performed on all FCBP
- Vital signs and weight
- Complete physical examination
- Clinical laboratory evaluations
- Subject Daily Diary Assessment
- CDAI assessment
- Ileocolonoscopy (if not already done within 8 weeks of the previous colonoscopy)

- Return and count IP

## 6.4. Follow-up Period

All subjects will be followed for 28 days after the last dose of IP for AE reporting, as well as SAEs made known to the Investigator at any time thereafter that are suspected of being related to IP, as described in Section 10.1.

Subjects who complete the Week 52 Visit, as well as subjects who prematurely discontinue from the study, will have a 4-week Follow-up Visit. If the ET Visit occurs 28 days or more after the last dose of IP, then the Follow-up Visit is not required.

Subjects entering the Long-term Extension Study will not have the Follow-up Visit.

The following evaluations will be performed at Follow-up Visit:

- Prior and concomitant procedures
- Prior and concomitant medications
- AE evaluation
- Vital signs and weight
- A urine pregnancy test will be performed on all FCBP
- Limited physical examination
- Clinical laboratory evaluations
- Subject Daily Diary assessment
- CDAI assessment

## 6.5. Safety Assessments

### 6.5.1. Physical Examination

A complete physical examination will include evaluation of the skin, nasal cavities, eyes, ears, abdomen, and respiratory, cardiovascular, neurological, lymphatic, and musculoskeletal systems. Gynecological and urogenital examinations will not be performed unless for cause.

Limited physical examinations will include evaluation of the skin, abdomen, and respiratory, cardiovascular, lymphatic, and musculoskeletal systems.

An abdominal examination will be performed at every visit (including those visits at which a complete or partial physical examination is not being performed) to assess the presence of an abdominal mass for the CDAI calculations.

### 6.5.2. Electrocardiogram

Subjects will have a 12-lead electrocardiogram (ECG) at the frequency specified in Table 3. Sites are to use their own local ECG machines and the automated ECG readings will be further interpreted by the Investigator by clinically correlating them with the subject's condition. The Investigator's clinical interpretation will be recorded in the eCRF as: normal; abnormal, not clinically significant; or abnormal, clinically significant.

### 6.5.3. Clinical Laboratory Assessments

Clinical laboratory evaluations will be performed by a central laboratory to include the following laboratory assessments performed at the frequency specified in [Table 3](#):

- Hematology panel will include: complete blood count (CBC) with differential, including red blood cell (RBC) count, hemoglobin, hematocrit, mean corpuscular hemoglobin (MCH), mean corpuscular hemoglobin concentration (MCHC), mean corpuscular volume (MCV), white blood cell (WBC) count (with differential), and platelet count.
- Serum chemistry panel will include: total protein, albumin, calcium, phosphorous, glucose, total cholesterol, triglycerides, uric acid, total bilirubin, alkaline phosphatase, aspartate aminotransferase (AST)/serum glutamic oxaloacetic transaminase (SGOT), alanine aminotransferase (ALT)/serum glutamic pyruvic transaminase (SGPT), sodium, potassium, chloride, carbon dioxide, blood urea nitrogen (BUN), creatinine, lactic dehydrogenase (LDH), magnesium, and complement activation (Bb, C3a and C5a).
- Coagulation assessment will include: prothrombin time (PT) and activated partial thromboplastin time (APTT)
- Urinalysis will be done at the central lab and will include specific gravity, pH, glucose, ketones, protein, blood, bilirubin, leukocyte esterase, nitrite, and urobilinogen. Microscopic urinalysis (bacteria, casts, crystals, epithelial cells, RBC, and WBC) will be performed only if the dipstick urinalysis is abnormal.

Clinical laboratory evaluations are not required to be fasting. However, the site will record whether a clinical laboratory evaluation was fasting or nonfasting on the lab requisition form.

In subjects who develop new changes in liver function tests (eg, ALT or AST > 2 x the upper limit of normal [ULN], or Total Bilirubin [TBL] > 1.5 x ULN with normal baseline values, or  $\geq 2$  x the baseline values in subjects with abnormal baseline values), repeat testing should be performed within 48 to 72 hours. If abnormalities persist, subjects should be evaluated for causes of new elevations in ALT/AST or TBL (including but not limited to tests for hepatitis, liver imaging, history of Gilbert's syndrome). If there are persistent elevations in ALT or AST and/or TBL then close observation (including laboratory testing as appropriate) should be initiated and treatment could be temporarily interrupted or discontinued. Discontinuation or temporary interruption of study treatment should occur when criteria delineated in [Appendix O](#) are met. After treatment discontinuation or interruption, assessments should continue until a return of aminotransferases and/or TBL to normal or baseline levels, or until alternative explanation for the abnormal liver function tests (LFTs) is found.

### 6.5.4. Stool Assessment

Stool culture analysis and assessment of Clostridium (C.) difficile toxin will be performed at the Screening Visit. Subjects who are stool positive for any enteric pathogen or C. difficile toxin at the Screening Visit, will be excluded from the study. Subjects who are initially positive for C. difficile toxin may re-screen for the study 8 weeks after the start of therapy, provided that the toxin results for C. difficile are negative.

### **6.5.5. Clinically Significant Abnormal Findings**

Clinically significant abnormal findings (clinical laboratory assessments, physical examination, ECG), with exception to the disease under study (CD), identified prior to first dose of IP will be recorded on the eCRF as medical history; clinically significant findings after the first dose of IP will be recorded as AEs.

### **6.5.6. Contraception Education**

Counseling about pregnancy precautions and the potential risks of fetal exposure must be conducted for FCBP. The Investigator will educate all FCBP about the different options of contraceptive methods and their correct use at the Screening and Baseline Visits. The subject will be re-educated every time her contraceptive measures/methods or ability to become pregnant changes. The female subject's chosen form of contraception must be effective by the time the female subject is randomized into the study (for example, hormonal contraception should be initiated at least 28 days before baseline). A female of childbearing potential taking an oral contraceptive may need a backup or an alternative method of birth control based on Investigator judgment as the subject's Crohn's disease may potentially decrease the effectiveness of oral contraceptives.

There are no data on the effects of GED-0301 in pregnant women and data in animals are limited. Results of the animal and in vitro studies can be found in the IB. All FCBP must use 1 of the approved contraceptive options as described in the eligibility criteria while on IP and for at least 28 days after administration of the last dose of the IP. At the time of study entry, and at any time during the study when a subject's contraceptive measures or ability to become pregnant changes, the Investigator will educate the subject regarding contraception options and correct and consistent use of effective contraceptive methods in order to successfully prevent pregnancy.

## **6.6. Efficacy Assessments**

### **6.6.1. Subject Daily Diary**

During the Screening Visit, an electronic subject diary device will be given to each subject. The subject will receive instructions by the site personnel pertaining to the use of the electronic device and the importance of diary compliance throughout the study. On an ongoing basis, site personnel are expected to provide education and support to the subject about the use of the electronic device. In order to achieve consistent daily diary recording, the subject is instructed by the site personnel (at each visit if necessary) that he/she should enter diary data, each day, continuously throughout the study. Site personnel must also assess the subject's compliance with reporting of the daily diary data entries throughout the study.

The daily diary data will be extracted from the electronic devices and used for calculation of the CDAI efficacy parameters.

The electronic subject diary device will record the following information for the subject to assess his/her CD activity each day:

- Number of liquid or very soft stools per 24 hours
- Abdominal pain/cramps

- General well-being
- Fever over 100°F (37.8°C)
- Use of diphenoxylate/atropine, loperamide, or opiates for diarrhea

### 6.6.2. Crohn's Disease Activity Index

The CDAI ([Appendix D](#)) is the most commonly used measure in clinical studies evaluating the efficacy of new therapies in CD patients with predominantly inflammatory disease ([Best, 1976](#); [Sandborn, 2002](#)). The daily diary will assess how CD affects the subject's quality of life and the effect of treatment on CD activity. The CDAI consists of a questionnaire with responses scored numerically and weighted. Scores (range 0 to 600) are then ranked according to severity of the disease. Mild active disease is defined by a score of  $\geq 150$  and  $\leq 219$ , moderate active disease is defined by a score of  $\geq 220$  and  $\leq 450$ , and severe disease is defined as a CDAI score  $> 450$ . Remission is defined as a CDAI score  $< 150$ .

The CDAI consists of 8 variables:

1. Total number of liquid or very soft stools (total for previous 7 days)
2. Abdominal pain/cramps rating (total for previous 7 days)
3. General well-being rating (total for previous 7 days)
4. Total number of listed categories the subject has experienced during the last 7 days
  - Arthritis or arthralgias
  - Iritis/uveitis
  - Erythema nodosum, pyoderma gangrenosum, or aphthous ulcers
  - Anal fissures, fistulae, or abscess
  - Other fistula (specified by site personnel)
  - Fever higher than 100°F or 37.8°C during previous week
5. Antidiarrhea drug therapy taken (eg, loperamide, diphenoxylate, or opiates)
6. Abdominal mass presence
7. Anemia based on hematocrit value entered into formula:
  - a. For men =  $47 - \text{hematocrit value}$
  - b. For women =  $42 - \text{hematocrit value}$
8. Body weight in kilograms (kg) entered into formula:  
$$([\text{standard weight in kg} - \text{actual weight kg}] / [\text{standard weight in kg}]) \times 100\%$$

[Redacted]

[Redacted]

[Redacted]

[Redacted]

[Redacted]

[Redacted]

[Redacted]

[Redacted]

- [Redacted]
- [Redacted]
- [Redacted]
- [Redacted]
- [Redacted]
- [Redacted]
- [Redacted]
- [Redacted]
- [Redacted]
- [Redacted]

[Redacted]

[Redacted]

[Redacted]

CEL GENE PROPRIETARY INFORMATION

### 6.6.5. Ileocolonoscopy

All eligible subjects are required to have ileocolonoscopies performed during the Screening Period, Week 12, and Week 52. The screening ileocolonoscopy should be performed if the subject's screening CDAI score is  $\geq 220$  and  $\leq 450$ .

Subjects who discontinue from the study prior to the Week 52 Visit, will have the ileocolonoscopy done at the ET Visit, if an ileocolonoscopy has not been performed within 8 weeks of the previous ileocolonoscopy.

Video images of all endoscopic procedures will be captured and sent to a qualified centralized reader for calculation of the SES-CD to assess subject eligibility at screening, and to assess efficacy at Weeks 12 and 52. Additionally, the local SES-CD will be collected from the investigational sites. The site will receive a central reader SES-CD report during the Screening Period to determine if the SES-CD inclusion criterion is met.

For subjects at increased risk for colorectal cancer, pan-colonic surveillance with colonoscopy and biopsies should be done according to local guidelines.

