| Inclusion / Exclusion Criteria       | X                | X                             | -          | -          | -               | -          | -          | -          | -          | -          | -          | -          | -          | -          | -               | -               | -  |
| Medical History                      | X                | -                             | -          | -          | -               | -          | -          | -          | -          | -          | -          | -          | -          | -          | -               | -               | -  |
| Prior / Concomitant Medications      | X                | X                             | X          | X          | X               | X          | X          | X          | X          | X          | X          | X          | X          | X          | X               | X               | X  |
| Prior / Concomitant Procedures       | X                | X                             | X          | X          | X               | X          | X          | X          | X          | X          | X          | X          | X          | X          | X               | X               | X  |
| Adverse Events                       | X                | X                             | X          | X          | X               | X          | X          | X          | X          | X          | X          | X          | X          | X          | X               | X               | X  |
| Pregnancy Test e          | X                | X                             | -          | -          | X               | -          | -          | -          | -          | -          | -          | -          | -          | -          | -               | X               | X  |
| Contraception Education f | X                | X                             | -          | -          | -               | -          | -          | -          | -          | -          | -          | -          | -          | -          | -               | -               | -  |
| Vital Signs / Weight                 | X                | X                             | X          | X          | X               | X          | X          | X          | X          | X          | X          | X          | X          | X          | X               | X               | X  |

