| Clinical Lab (Chemistry) g  | X                | X                             | -          | -          | X               | -          | X          | -          | X          | -          | X          | -          | X          | -          | X               | X                | X  |
| Clinical Lab (Urinalysis) g   | X                | X                             | -          | -          | X               | -          | X          | -          | X          | -          | X          | -          | X          | -          | X               | X                | X  |
| Efficacy Assessments  |                  |                               |            |            |                 |            |            |            |            |            |            |            |            |            |                 |                  |  |
| Subject Diary h
Instruct use of electronic device/assess compliance | X                | X                             | X          | X          | X               | X          | X          | X          | X          | X          | X          | X          | X          | X          | X               | X                | X  |
| CDAI i  | X i   | X                             | X          | X          | X               | X          | X          | X          | X          | X          | X          | X          | X          | X          | X               | X                | X  |
| Ileocolonoscopy j   | X                | -                             | -          | -          | X               | -          | -          | -          | -          | -          | -          | -          | -          | -          | X               | X                | -  |

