**Dosing**

|                     |   |   |   |   |   |   |   |   |   |   |   |   |   |   |   |   |   |   |
|---------------------|---|---|---|---|---|---|---|---|---|---|---|---|---|---|---|---|---|---|
| Dispense IP         | - | X | X | X | X | X | X | X | X | X | X | X | X | X | X | - | - | - |
| Return and Count IP | - | - | X | X | X | X | X | X | X | X | X | X | X | X | X | X | X |   |

CDAI = Crohn's Disease Activity Index; ECG = Electrocardiogram; ET = Early Termination Visit; ; FCBP = females of childbearing potential; ; IP = investigational product; NA = not applicable; ; Sc= Screening; ; V1 = Visit 1;

a Subjects who prematurely discontinue from the study at any time other than the Week 12 Visit and prior to the last scheduled study visit, including subjects who enter the Long-term Active-treatment Study (GED-0301-CD-004), will complete the Early Termination (ET) Visit (Section 6.3). The ET Visit should be completed as soon as possible after the decision is made to permanently discontinue the study treatment. Subjects who discontinue from the study at Week 12 will complete the Week 12 Visit.  
b Subjects who complete the Week 52 Visit, as well as subjects who prematurely discontinue from the study, will have a 4-week Follow-up Visit (Section 6.4). If the ET Visit occurs ≥ 28 days after the last dose of IP, then the Follow-up Visit is not required. Subjects entering the Long-term Extension Study will not have the Follow-up Visit.

- c At the Week 12 Visit and thereafter, until the Week 52 Visit, subjects [REDACTED], will be eligible to early escape into the Long-term Active-treatment Study (GED-0301-CD-004), or may discontinue from the study. In order to be considered for the early escape at [REDACTED]. Due to the delay in receiving the hematocrit sample results, beginning at the Week 12 Visit, and throughout the remainder of the study, the CDAI score will be evaluated by the site using the hematocrit results from the previous visit.
- d Subjects who complete the GED-0301-CD-002 study at the Week 52 Visit, will have the option to enter the Long-term Active-treatment Study. Subjects entering the Long-term Extension Study will not have the Follow-up Visit.
- e Pregnancy testing will be performed for FCBPs. Serum pregnancy tests will be performed at screening and urine pregnancy will be done at the remaining visits as described in Table 3.

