- f Contraception education is for Females of Child Bearing Potential (FCBP). The Investigator will educate all FCBP about the different options of contraceptive methods and their correct use at Screening and Baseline Visits. The subject will be re-educated every time her contraceptive measures/methods or ability to become pregnant changes. The female subject's chosen form of contraception must be effective by the time the female subject is randomized into the study (for example, hormonal contraception should be initiated at least 28 days before baseline).
- g Details pertaining to clinical labs are provided in Section 6.5.3.
- h The electronic Subject Daily Diary (Section 6.6.1) will be provided to subjects at the Screening Visit. Subject compliance with the completion of diary data should be assessed at each study visit during the Screening and Double-blind Treatment Period.
- i The screening CDAI (Section 6.6.2) will be based on the Subject Daily Diary data collected during the Screening Period. Note that an abdominal exam is needed for CDAI assessment.
- j The screening ileocolonoscopy should be performed following confirmation of the subject's eligibility, based on the CDAI score. Follow-up ileocolonoscopies will be done at Week 12 and Week 52 (Section 6.6.5). The ET ileocolonoscopy will not be repeated if performed within 8 weeks of the previous ileocolonoscopy.
- [REDACTED]

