## 6.2. Double-blind Treatment Period

The subject will begin study treatment upon confirmation of eligibility. For all subsequent visits in the Double-blind Treatment Period, an administrative window of  $\pm 3$  days is permitted. The following evaluations will be performed at the frequency specified in Table 3. The evaluations should be performed prior to dosing on the visit day, unless otherwise specified.

- Prior and concomitant procedures
- Prior and concomitant medications
- AE evaluation (continuously assessed)
- Electrocardiogram at the Week 12 and Week 52 Visits
- Contraception education (Section 6.5.6) at the Baseline Visit (Visit 2)
- A local urine pregnancy test will be performed on all FCBP. All local urine pregnancy test kits will be provided by the central laboratory. Urine and serum pregnancy tests should be performed if the FCBP has missed a menstrual period or the contraception method has changed at any time during the study.
- Vital signs and weight
- Complete physical examination (Section 6.5.1) at the Week 12 and Week 52 Visits
- Limited physical examination (Section 6.5.1) at the Baseline Visit, Week 24, and Week 36 Visits

- An abdominal examination to assess for the presence of an abdominal mass for the CDAI calculation will be performed at every visit. (Section 6.5.1)
- Clinical laboratory evaluations
- Subject Daily Diary Assessment
- CDAI assessment
  - Due to the delay in receiving the hematocrit sample results, beginning at the Week 12 Visit and thereafter until the Week 52 Visit, the CDAI score will be evaluated by the site using the hematocrit results from the previous visit.
- Ileocolonoscopy for SES-CD should be performed within the Visit window at Week 12 and Week 52.

[REDACTED]

- Dispense IP: The Principal Investigator (PI), Sub-investigator (Sub-I), or Study Coordinator (SC) should make an effort to witness subjects taking their first dose and record the date and time in the source document record. The IP (four tablets) should be taken QD by the subjects. Subjects will be instructed to take the IP in the morning, 30 minutes before breakfast, with a glass of water, and they will also be instructed to refer to the label for storage instructions.

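### Week 52 has a required ileocolonoscopy but no scheduled pregnancy test, a minor gap that one urine test would close

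*Protocol*

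**What the plan says.** Section 6.6.5 of the Protocol makes ileocolonoscopy compulsory at three points: "All eligible subjects are required to have ileocolonoscopies performed during the Screening Period, Week 12, and Week 52". Section 8.3 names it again as a required procedure. Section 6.2 sets the on-treatment timing: "Ileocolonoscopy for SES-CD should be performed within the Visit window at Week 12 and Week 52". Subjects who leave early have one at the Early Termination (ET) Visit, subject to footnote j of Table 3: "The ET ileocolonoscopy will not be repeated if performed within 8 weeks of the previous ileocolonoscopy".

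Routine pregnancy testing is governed by Table 3. Its "Pregnancy Test e" row is marked at Screening, Baseline, Week 12, ET and Follow-up, and shows a dash at Week 52. Footnote e refers back to the table: "Serum pregnancy tests will be performed at screening and urine pregnancy will be done at the remaining visits as described in Table 3". The testing item in Section 6.2 also follows the Table 3 frequency, and Sections 6.3 and 6.4 repeat the urine test for ET and Follow-up.

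Outside the schedule, Section 6.2 has a for-cause rule: "Urine and serum pregnancy tests should be performed if the FCBP has missed a menstrual period or the contraception method has changed". Sections 4.2 and 6.5.6 require approved contraception while on investigational product (IP) and for at least 28 days after the last dose. Section 6.4 exempts subjects entering the long-term study from the Follow-up Visit.

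**The concern.** FCBP who complete the study undergo a compulsory invasive procedure at Week 52, and the plan provides no routine pregnancy result before it. At the other visits with an ileocolonoscopy, a test is on the schedule. The Follow-up test cannot fill the gap: it comes after the procedure, and completers who continue into the long-term study do not have that visit.

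What is at stake is subject safety at one visit: an unrecognised pregnancy could go unscreened before a required procedure. There is a secondary reporting aspect. Section 10.4.1 makes pregnancies on IP, or within at least 28 days of the last dose, immediately reportable. A completer who rolls over takes IP up to Week 52 with no routine test in this study after Week 12.

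**Working it through.** The plan states no figure for this point, so the check is a reading of Table 3 followed by a subtraction.

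**Step 1: alignment.** Table 3 has 17 visit columns (Screening, Baseline, Weeks 4 to 52 in 4-week steps, ET, Follow-up). The pregnancy-test row and the "Ileocolonoscopy j" row each have 17 cells, so both can be read column by column. The complete physical examination and ECG rows, each marked at both Week 52 and ET, confirm where those columns fall.

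**Step 2: the two rows side by side.**

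| Visit | Pregnancy test | Ileocolonoscopy |
|---|---|---|
| Screening | X | X |
| Baseline | X | – |
| Week 12 | X | X |
| Week 52 | – | X |
| ET | X | X |
| Follow-up | X | – |
| All other weeks | – | – |

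Four visits carry an ileocolonoscopy and three of them carry a pregnancy test. Week 52 is the only exception.

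**Step 3: interval since the last routine test.** 52 − 12 = 40 weeks, or 40 × 7 = 280 days. With ±3 days at each end the range is 280 ± 6 = 274 to 286 days, or 39.1 to 40.9 weeks.

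**Step 4: what follows Week 52.** Without rollover, the next test is at Follow-up, 4 weeks after the last dose and so after the procedure. With rollover, there is no Follow-up Visit, so Week 12 is the last scheduled test in this study.

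**Step 5: whether another provision supplies a result.**
- Contraception (4.2, 6.5.6) lowers the chance of pregnancy but does not detect one.
- For-cause testing (6.2) gives a result only if a missed period or a contraception change is noticed and reported.
- Unscheduled visits (6.2.1) need a reason to attend.
- Section 10.4.1 acts once a pregnancy is known or suspected.
- The latitude in Section 3.1.2 over which assessments to complete concerns subjects who withdraw or are discontinued, not completers.

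None of these gives a routine result before the Week 52 procedure.

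**Step 6: statistical cost of adding the test.** Table 5 gives 90% power for ER-50 at Week 52 (10% versus 20%, 266 per arm, two-sided 0.05). A two-group chi-square calculation reproduces it at 90.0%. Suppose k subjects per arm skip the procedure after a positive test, unrelated to response, and count as nonresponders. Each rate is then multiplied by (266 − k)/266:
- k = 1: 9.96% versus 19.92%, power 89.9%.
- k = 3: 9.89% versus 19.77%, power 89.6%.

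The values of k are assumptions, because the documents give no pregnancy counts. This step describes the cost of the fix and says nothing about the size of the gap.

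**The case against.** The strongest reply is that the protocol never links pregnancy testing to endoscopy. Baseline and Follow-up have a test and no procedure, and the visible pregnancy provisions concern IP: contraception on IP and for 28 days after, reporting over the same period, and stopping IP. On that reading the schedule is coherent. Tests come before first exposure, at Week 12, and about 28 days after the last dose. ET has its own test because ET can replace Follow-up. No visible passage says that ileocolonoscopy is hazardous in pregnancy, and the for-cause rule should catch a recognised missed period before Week 52.

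Much of this stands. A reader might infer from the three-of-four pattern, or from how closely the ET and Week 52 columns otherwise match, that the protocol has a pairing rule and broke it. The documents state no such rule, and ET's role as a substitute for Follow-up is a sufficient explanation for its test.

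The reply does not remove the gap. Even if the tests exist only to monitor IP exposure, completers who roll over take IP up to Week 52 with no scheduled test in this study after Week 12. The long-term protocol may test at entry, but it is not among the documents, and nothing visible here requires such a test before the Week 52 ileocolonoscopy.

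A reader might also infer that tests at Week 12 and ET can wrongly follow the procedure. The documents do not support a finding there: both visits carry a test, text next to the ileocolonoscopy item in Section 6.2 and next to footnote j is redacted, and the order within a visit is at most a missing detail.

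**Conclusion.** The point holds as a minor safety improvement. Week 52 is the one ileocolonoscopy visit without a scheduled pregnancy test, and the last routine test before it is 40 weeks earlier.

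The 40 weeks is the interval between routine tests. A reader might take it as the time a pregnancy could run undetected, but for-cause testing, the visits every 4 weeks and the abdominal examination at each visit make that unlikely. What remains is mainly an early, unrecognised or unreported pregnancy despite mandatory contraception. The documents give no number of FCBP, no pregnancy rate and no procedural risk figure, so expected cases or harm cannot be stated and none are assumed.

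The point also does not rest on a fetal drug hazard: Section 1.2.2.1 describes systemic bioavailability as negligible at up to 160 mg/day for 7 days. It affects no endpoint definition, alpha level or sample size.

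The conclusion rests on the visible text of Table 3 and Sections 6.2 to 6.6.5. It concerns the protocol as written, although the SAP records that the study was later stopped early.

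**What to change.** Add an X at Week 52 in the pregnancy-test row of Table 3. State in Section 6.6.5 or footnote j that, in FCBP, the local urine test is done and its result read before the Week 52 ileocolonoscopy, which is not performed if the result is positive. Section 6.2 and footnote e already refer to Table 3 and need no other change.

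The cost is one urine test per FCBP. The central laboratory already supplies the kits (Section 6.2), and urine is already collected at Week 52 (the "Clinical Lab (Urinalysis) g" row of Table 3).

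A subject who tests positive and skips the procedure would have no Week 52 SES-CD. She would count as a nonresponder for ER-50 and endoscopic remission under Protocol Section 9.6.1, and under SAP Section 11.2.2.1 if she is in its denominator. With the assumed 1 to 3 such subjects per arm, ER-50 power falls by 0.1 to 0.4 percentage points. The sample size stays as it is.
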